### **Potential Risks:**

There will be little or no long-term risk expected from participation in this research project. Since there are multiple blood draws, they will be done by an experienced registered nurse who is working in the ER so that the pain and discomfort will be minimal. And blood draws will be done using aseptic techniques. No risk is anticipated for eating breakfast containing eggs or from RFPM or questionnaires for food intake.

As with any research study, there are risks for breach of confidentiality. To mitigate this risk the master list of participant names and corresponding participant codes will be stored separately and securely from the electronic research database in the locked office in a secure locked filing cabin (i.e. behind 2 locks per HIPPA standards for patient records). There will be no personal identifying information in the research database; therefore, participants cannot be identified from that source. All electronic files containing participant identifying data will be password protected and stored on digital recording media in separate locations (in locked filing cabinets behind locked doors) at TTU. The participant signed Informed Consent will be similarly stored.

The participants will be informed of the right to withdraw from the study at any point. The participants who withdraw will be provided with compensation and other benefits for the time spent up to the point of withdrawal. The participants will be provided with access to the study personnel and the PI throughout the period of intervention via telephone, text messaging or email. If an unexpected non-emergent adverse event is to occur, the participants will be referred to a health care facility. For any urgent health concerns, participants will be instructed to dial 911

for immediate help. If an unexpected medical event occurs during the study visits, the subjects will be immediately referred to the nearest medical facility. All study staff have current Basic Life Support CPR training. The IRB will be notified regarding any adverse events that occur during the study.

### **Potential Benefits:**

Participants will learn about their blood sugar, insulin and satiety hormone values. They will also learn about their resting metabolic rate.

### **Subject Compensation**

Participants in the study will be compensated \$100 for participation. Subjects will receive \$25 for the 1st visit. Once subjects send all the photos of what they have consumed for all 7 days they will receive another \$50 (\$7 for each day). Finally, subjects will receive \$25 for 2nd visit. If a subject begins any visit and is unable to complete it, \$10 will be rewarded. Ten dollars will be awarded if a subject cannot complete all the VAS or stay for all the blood draws or consume test breakfasts.

On each of these designated days, subjects' will be required to fill out the required paperwork to receive compensation. Our research team will follow the guidelines stated in OP 62.25 *Payments to Research Participants*, and all subject information gathered to receive compensation will be kept confidential. The grant received from the Egg Nutrition Center will cover subject compensation

### **Adverse Events and Liability**

The proposed research study only contains minimum risk beyond ordinary life circumstances. Some unexpected adverse effects that are possible in this study are related to IV catheter insertion and removal. A trained certified registered nurse will take all precautions to minimize any adverse events regarding the blood-sampling component of this study. The participants will be provided with the phone number and email of the study PI and also email contact information for non-urgent concerns and or adverse events reporting. For urgent medical concerns, participants will be directed to contact their healthcare provider or visit local urgent care facilities (contact information will be provided during the enrollment process). For medical

emergencies, the participants will be instructed to dial 911. The TTU IRB will be notified per TTU reporting guidelines regarding any adverse events that occur during the study.

### **Informed Consent Form (ICF)**

Please see attached consent form in Appendix C on pages 27 to 32.

## Appendix A-1: Recruitment Announcement

### TechAnnounce Advertisement

#### **Non-Diabetic Individuals Needed for a Study on Dietary Patterns Using Remote Food Photography Method (RFPM).**

Texas Tech University Department of Nutritional Sciences

##### **What will I be asked to do?**

You will be required to visit our facility in the morning for two days. There will be several blood draws using a iv catheter and filling in some questionnaires. You will be given a test breakfast and trained to use food photography. For seven days, you will have to take photographs of what you have eaten throughout the day using smart phones.

##### **You can be considered to participate in this study if:**

1. You are a male or female within the ages of 18-65 years of age.

2. You are within the BMI range of 20-60 kg/m^2.
3. You have not lost weight  $\geq 5\%$  in the past 3 months.
4. You are not a patient with diabetes.

Compensation of \$100 for your time (two visits) is included.

Transportation to our clinic will not be provided and all participation is completely confidential. Your participation in this study is greatly appreciated and you can stop participating at any time during the study if you so desire.

For more information or if you are interested in participating, please contact [name] Graduate Teaching Assistant, at [[contact]](mailto:[contact]) or by phone at [contact].

*This study has been approved by the TTU Institutional Review Board.*

## Appendix A-2 Recruiting Announcement- Flyer

# Non-Diabetic Individuals Needed for a Study on Dietary Patterns Using Remote Food Photography Method (RFPM).

Texas Tech University Department of Nutritional Sciences

### What will I be asked to do?

You will be required to visit our facility in the morning for the first visit and there will be several blood draws using an iv catheter and filling in some questionnaires. You will be given a test breakfast and trained to use food photography. For seven days, you will have to take photographs of what you have eaten throughout the day using smart phones. After seven days, you will be required to visit the facility again and have the second test meal, several blood draws and filling in some questionnaires.

### You can be considered to participate in this study if:

1. You are a male or female within the ages of 18-65 years of age.
2. You are within the BMI range of 20-60 kg/m^2.
3. You have not lost weight  $\geq 5\%$  in the past 3 months.
4. You are not a patient with diabetes.

Compensation of \$100 for your time (two visits) is included.

Transportation to our clinic will not be provided and all participation is completely confidential. Your participation in this study is greatly appreciated and you can stop participating at any time during the study if you so desire.

**For more information or if you are interested in participating, please contact [name], Graduate Research Assistant, at [[contact]](mailto:[contact]) or by phone at [contact].**

**Thank You!**

*This study has been approved by the TTU Institutional Review Board.*

RFPM Research Study  

## Appendix B: Telephone Screening Interview Protocol

Hello, during this conversation, we are going to give you information about the study and also ask you some questions. Please respond carefully. Once the telephone interview is complete, we will review your information with the study team to determine if you are eligible. You will be informed of the outcome within **48 hours** of this call and if you are eligible, scheduled for your first appointment. Your responses here are confidential within the study team and you are in no way obligated to participate by completing this prescreening.

**Name:** \_\_\_\_\_

**Phone:** \_\_\_\_\_

**Email:** \_\_\_\_\_

**Age:** \_\_\_\_\_ **Gender:** M  F

**Height:** \_\_\_\_\_ **Weight:** \_\_\_\_\_

**BMI:** \_\_\_\_\_

(Research personnel will use given height and weight to calculate BMI)

**How did you hear about this study?** \_\_\_\_\_

This call will last approximately 30 minutes. If at any point, you have any questions or do not wish to continue, please tell me so. The purpose of this study is to study on usual dietary patterns using remote food photography method (RFPM). You will be required to visit our facility in the morning for the first visit and there will be several blood draws and questionnaires. You will be given a test breakfast and trained to use SmartIntake© smartphone “app” used in food photography. For seven days, you will have to take photographs of food including snacks before eating and of the leftovers, using smart phones. After seven days, you will be required to visit the facility again and have the second test meal. There will be several blood draws on the second visit.

**Would you like to learn more about the study and see whether you would be eligible to participate? Y N.**

**If No:** Thank you very much for your time, may we keep your contact information on file to inform you of future studies?

**If Yes:** Ok good. Let's continue.

- a) For your participation in this study you will be compensated for your time. After this phone interview, if you are eligible, you will be scheduled for the first visit. Upon completion of the first and second visits and sending photographs of what you have eaten on all 7 days and maintaining a food record you will be eligible to receive \$100.
- b) If you are determined to be eligible, the first visit will be scheduled for a date within the next couple of weeks. The first visit will last approximately 4 hours. First, we will have you sign some papers (Informed Consent). At this visit you will have body weight, height, waist and hip circumference measured along with blood pressure. You will be offered a test breakfast and train to take photographs of food using smart phones.
- c) There will be several blood draws via IV catheter and filling up of questionnaires. For blood draws a trained registered nurse will insert an IV catheter, which is small needle and a tube. After insertion of IV catheter, the needle will be removed leaving the plastic tube for 3 hours. We will take one blood sample before and five blood samples after breakfast. Since we leave the IV catheter inserted till the blood withdrawal is over you will have one needle stick per visit. If iv-catheterization fails at some point, which happens very rarely we will take blood from separate needle sticks every half an hour. However, there will be total of 4 needle sticks including the initial needle stick done to insert the IV catheter applied in a single visit if the IV catheterization fails.
- d) You will be asked to take photographs of all the meal including the snacks for 7 days. You have to take photographs before and after (the left overs) you have taken each meal.
- e) On day 1 of the seven days we will contact you through phone to assess get a 24-hour recall of your energy intake.
- f) After 7 days, you will have to visit the facility for the 2nd visit.
- g) The second visit will last up to 4 hours and you will be given the second test meal. There will be several blood draws via an IV catheter as mentioned above.

Do you have any questions up to this point?

**Are you still interested in this study? If yes, I have some more questions.**      Y      N

### **Eligibility for the study**

1. Have you lost or gained more than 5% of your body weight in past 3 months?

Y                    N Current weight: \_\_\_\_\_ x.05= \_\_\_\_\_ 5% of CBW

2. Have you been involved in a formal weight loss program in the past 3 months?

Y                    N

3. Tell me what medications you are taking now (list) \_\_\_\_\_

---

4. Are you currently on or have been on within the past 4 weeks any anti-depressant, anti-epileptic, or anti-anxiety medicines? Y                    N

Which ones: \_\_\_\_\_

5. Have you experienced persistent loss of appetite, nausea or vomiting (last 4 weeks)?

Y                    N

6. Have you taken any weight loss medications in the past 4 weeks? Y                    N

List them: \_\_\_\_\_

7. Do you smoke? Y                    N

If No, when did you last smoke? Date: \_\_\_\_\_

8. Do you drink alcohol? Y    N

If Yes, how much and how often? \_\_\_\_\_

9. Do you have a history of substance or alcohol abuse? Y                    N

10. Do you currently have any of the following conditions?

Diabetes Mellitus                            Y                    N

Ischemic Heart disease                    Y                    N

Cerebrovascular accidents (strokes)                    Y                    N

Congenital heart disease                    Y                    N

Hypertension                                Y                    N

Polycystic ovary syndrome                Y                    N

Prader-Willi syndrome                    Y                    N

Major systemic illness                    Y                    N

Familial hyperlipidemia Y N  
Endocrine diseases (Cushing's syndrome,  
Grave's disease, Hashimoto's thyroiditis) Y N  
If Yes, please specify \_\_\_\_\_

11. Are you currently diagnosed with diabetes mellitus? Y N

12. Did you have any abnormal blood glucose report? Y N

If Yes, please explain: \_\_\_\_\_

13. Do you have any family history of diabetes mellitus? Y N

If Yes, please explain: \_\_\_\_\_

14. Do you have a history of eating disorders such as bulimia nervosa, anorexia nervosa, or binge eating disorder?  Y  N

If Yes, please describe: \_\_\_\_\_

15. If female, are you pregnant or lactating, or suspect you might be pregnant or currently trying to conceive? Y N

16. Do you have any allergies sensitivity to or dislike of eggs? Y N

17. How many eggs do you consume for a week? \_\_\_\_\_

18. Do you currently take vitamins or other over the counter 'remedies'? Y N

List: \_\_\_\_\_

19. Do you like and will you eat eggs? Y N

20. Do you like and will you eat Special K® Cereal?  Y  N

21. Do you like and will you consume skim milk?  Y  N

22. Do you like and will you consume 2% milk? Y N

23. Do you like and will you consume Silk® Original Soy Milk?  Y  N

24. Do you like and will you eat [name]® Extra Thin White Bread? Y N

25. Do you like and will you eat Nature's Own® Double Fiber Wheat Bread? Y N

26. Do you like and will you eat Arnold® Double Protein Whole Grain Bread? Y N

27. Do you like and will you eat butter?	Y	N
28. Do you like and will you eat margarine?	Y	N
29. Do you like and will you eat Smuckers® Strawberry Jam?	Y	N
30. Do you like and will you eat Smuckers® Sugar Free Strawberry Jam?	Y	N
31. Will you drink water or diet coke?	Y	N
32. Do you have an iPhone?	Y	N

If yes, are you willing to use your phone or do you want a separate phone to use in the study? \_\_\_\_\_

**Are you still interested in participating in this study?** Y N

If Yes, we will let you know whether you are eligible within 48 hours of this call and if you are eligible, scheduled for your first appointment. Thank you for your cooperation.

## Appendix D

### Data Collection Sheet

Subject ID: \_\_\_\_\_

Date: \_\_\_\_\_

Age: \_\_\_\_\_

Male:  Female:

Visit No: \_\_\_\_\_

#### Anthropometrics:

Height: \_\_\_\_\_

Weight: \_\_\_\_\_

Calculated BMI: \_\_\_\_\_

Use BMI formula:  $wt \text{ (kg)} / ht \text{ (m}^2\text{)}$

Waist Circumference: \_\_\_\_\_

Hip Circumference: \_\_\_\_\_

\_\_\_\_\_

\_\_\_\_\_

\_\_\_\_\_

\_\_\_\_\_

Avg: \_\_\_\_\_

Avg: \_\_\_\_\_

Blood Pressure: \_\_\_\_\_ mm Hg

#### Blood Draw, VAS, and Meal

Time IV Catheter is placed: \_\_\_\_\_

Time Fasting Blood Sample Taken: \_\_\_\_\_

Time of Fasting VAS: \_\_\_\_\_

Time of RMR: \_\_\_\_\_

RMR: \_\_\_\_\_

Time Breakfast Given (10 min. to eat): \_\_\_\_\_

Type of Breakfast:

Test Breakfast A

Test Breakfast B

Test Breakfast C

Test Breakfast D

Training for RFPM: \_\_\_\_\_

Postprandial Blood Draws, VAS and RMR (times of each) and values of RMR:

30 minutes: \_\_\_\_\_

VAS: \_\_\_\_\_

RMR: \_\_\_\_\_

60 minutes: \_\_\_\_\_

VAS: \_\_\_\_\_

RMR: \_\_\_\_\_

90 minutes: \_\_\_\_\_

VAS: \_\_\_\_\_

RMR: \_\_\_\_\_

120 minutes: \_\_\_\_\_

VAS: \_\_\_\_\_

RMR: \_\_\_\_\_

180 minutes: \_\_\_\_\_

VAS: \_\_\_\_\_

RMR: \_\_\_\_\_

Time of Food Frequency Questionnaire: \_\_\_\_\_

Time of IV Catheter Removal: \_\_\_\_\_

## Appendix E

### Visual Analog Scale (VAS) Questionnaire

Subject ID: \_\_\_\_\_

Date: \_\_\_\_\_

Age: \_\_\_\_\_

Male:  Female:

Visit No: \_\_\_\_\_

Instructions:

For each question, please make an up-and-down line at the point on the line that best describes

**1. How hungry do you feel at this moment?**

Not at all hungry

[figure not shown]
Extremely hungry

**2. How thirsty do you feel at this moment?**

Not at all thirsty

[figure not shown]
Extremely thirsty

**3. How full does your stomach feel at this moment?**

Not at all full

[figure not shown]
Extremely full

**4. How empty does your stomach feel at this moment?**

Not at all empty

[figure not shown]
Extremely empty

**5. How much do you think you could eat right now?**

Nothing at all

A large amount

## Appendix F

### Food Frequency Questionnaire

Subject ID: \_\_\_\_\_

Date: \_\_\_\_\_

Age: \_\_\_\_\_

Male:  Female:

#### GENERAL INSTRUCTIONS

- Answer each question as best you can. Estimate if you are not sure. A guess is better than leaving a blank.
- Put an X in the box next to your answer.
- If you make any changes, cross out the incorrect answer and put an X in the box next to the correct answer. Also, draw a circle around the correct answer.

1. How often do you eat **eggs, egg whites, or egg substitutes** (NOT counting eggs in baked goods and desserts)?

- 2 times per week
- 3–4 times per week
- 5–6 times per week
- 1 time per day
- 2 or more times per day

2. Each time you ate **eggs**, how many did you usually eat?

- 1 egg
- 2 eggs
- 3 or more eggs

3. How often were the eggs you ate **egg substitutes or egg whites only**?

- Almost never or never
- About  $\frac{1}{4}$  of the time
- About  $\frac{1}{2}$  of the time
- About  $\frac{3}{4}$  of the time
- Almost always or always

4. How often were the eggs you ate **regular whole eggs**?

- Almost never or never
- About  $\frac{1}{4}$  of the time
- About  $\frac{1}{2}$  of the time
- About  $\frac{3}{4}$  of the time
- Almost always or always

5. How often were the eggs you ate **cooked in oil, butter, or margarine**?

- Almost never or never
- About  $\frac{1}{4}$  of the time
- About  $\frac{1}{2}$  of the time
- About  $\frac{3}{4}$  of the time
- Almost always or always

6. How often were the eggs you ate part of **egg salad**?

- Almost never or never
- About  $\frac{1}{4}$  of the time
- About  $\frac{1}{2}$  of the time
- About  $\frac{3}{4}$  of the time
- Almost always or always

7. How often do eat eggs for your breakfast?

- Almost never or never
- About  $\frac{1}{4}$  of the time
- About  $\frac{1}{2}$  of the time
- About  $\frac{3}{4}$  of the time
- Almost always or always

8. How often do you eat eggs with bacon?

- Almost never or never
- About  $\frac{1}{4}$  of the time
- About  $\frac{1}{2}$  of the time
- About  $\frac{3}{4}$  of the time
- Almost always or always

9. How often do you eat eggs with hash browns?

- Almost never or never
- About  $\frac{1}{4}$  of the time
- About  $\frac{1}{2}$  of the time
- About  $\frac{3}{4}$  of the time
- Almost always or always

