### **F. Food Frequency Questionnaire**

Food frequency questionnaire (FFQ) adapted from diet history questionnaire (DHQ) by national cancer institute, to identify subjects belonging to quartiles for egg consumption. Number of eggs eaten per week will be determine based on FFQ. This will be given on the first visit.

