### **D. Research plan**

**Overview:** Subjects who routinely eat eggs will be recruited. Their food consumption pattern will be assessed by food frequency questionnaire (FFQ), to identify subjects belonging to quartiles for egg consumption. Number of eggs eaten per week will be determine based on FFQ. This will allow us to identify low and high consumers of eggs (bottom vs top quartile for egg consumption per week). Next, the RFPM, - a highly validated and innovative approach that uses camera-enabled Smart phones with data transfer capability [19] will be used to accurately assess food intake during all meals and snacks for 7 days. The RFPM will quantitate and compare the daily intake of saturated fat and energy, and saturated fat intake accompanying eggs between low and high egg consuming individuals.

**Subjects:** Inclusion criteria: 40 non-diabetic individuals (fasting glucose < 126 mg/dL), male or female, BMI  $\geq 20$  and  $\leq 60$  kg/m^2, Age: 18 – 65 y, Weight loss < 5% in the past 3 months. Exclusion: Diabetes, on diabetes medication, pregnant or lactating females, those with a history of gestational diabetes, have an unstable cardiac condition, a major systemic illness, a history of drug abuse or eating disorders, have uncontrolled hypothyroidism, have familial hyperlipidemias, allergies sensitivity to or dislike of eggs, consumption of < 1 egg per week, or attempting to lose weight.

[figure not shown]
**Approach:** After determining eligibility and obtaining informed consent, the eligible subjects will come to TTU clinic on at about 8 AM after an overnight fast. Blood test for HbA1c and fasting glucose be determined by the finger stick method. Next, each subject will be offered a standardized breakfast (e.g. bagel, 4 tsp cream cheese, 6 oz non-fat yogurt, 1 fruit (apple), 8 oz fruit juice), provided a smartphone and trained to photograph their food intake, using the smartphone provided. They will record all meals for the next 7 days (consumed under free living conditions) and the RFPM technology will be used to quantitate and analyze energy intake and macronutrients.

**Outcome measures:** Age, baseline BMI, HbA1c, waist circumference, baseline fasting glucose, per meal, daily and 7-d intake of energy, saturated fat, cholesterol, and eggs.

[figure not shown]

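### The FFQ cannot record once-weekly egg intake, which is eligible, so people can be tied or misplaced at the low-group cut in primary outcomes 2 and 4

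*Combined protocol and SAP*

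**What the plan says.** **Who is eligible.** The exclusion list under Recruitment and the Subjects paragraph of the 40-subject research plan in the same document set the same limit: "consumption of < 1 egg per week" is an exclusion. A person eating exactly 1 egg a week may therefore enrol.

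**What the form can record.** Appendix F, item 1, asks about "eggs, egg whites, or egg substitutes" together. The printed answers run from "2 times per week" up to two or more times a day. The form's instructions prefer an estimate to an empty item. Item 2 asks for eggs per occasion (1, 2, or 3 and above). Items 3 and 4 ask, in quarters, what share were "egg substitutes or egg whites only" and what share were "regular whole eggs".

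**What the form is used for.** Procedures, section F, says the FFQ serves "to identify subjects belonging to quartiles for egg consumption" and that "Number of eggs eaten per week will be determine based on FFQ". Primary outcomes 2 and 4 name the FFQ as the source of the high and low groups, and secondary outcome 6 (HbA1c) uses the same contrast. The SAP compares top and bottom quartiles of egg consumption without naming the source. Hypothesis 2 can be read as forming the quartiles from the food photographs (RFPM).

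**What is not stated.** No section gives a rule for turning items 1 to 4 into eggs per week, or for ties at a quartile cut.

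**The concern.** The lowest quartile is defined at the end of the scale where the form cannot record the truth. A once-weekly eater who follows the instructions will most naturally tick the lowest box, which doubles the true frequency. If that frequency is then multiplied by eggs per occasion, the error in eggs per week grows with portion size, and a light eater can move past a heavier one.

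At stake is who belongs to the low group in two of the six primary outcomes and one secondary outcome. With 48 subjects the extreme quartiles hold 48/4 = 12 people each, so one misplaced person is 1/12, about 8% of a group.

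**Working it through.** **Plan's own figures.** The plan gives no figure for the FFQ ranking. Its only power statement (40 subjects, effect size 0.45, level 0.05, at least 80%) reproduces as a paired comparison: 0.45 × √40 = 2.85, and Φ(2.85 − 1.96) = 81% by normal approximation (79% by noncentral t, two-sided). It is not in dispute here and does not describe a quartile contrast.

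**Inputs from the documents.** Lowest eligible intake 1 egg/week; lowest printed frequency 2/week; eggs per occasion 1, 2 or 3; N = 48.

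**Assumptions of this check.** Score = frequency × eggs per occasion. Frequencies are coded 2, 3.5, 5.5, 7 and 14 per week (midpoints for the two ranges, 14 for the open top class), and the top portion class is coded 3. A once-weekly eater ticks the lowest box.

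**Step 1: enumeration.**

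| Once-weekly portion | True eggs/week | Score | Ties with someone eating more | Ranks above someone eating more |
|---|---|---|---|---|
| 1 egg | 1 | 2 × 1 = 2 | 2 × 1 = 2 | none |
| 2 eggs | 2 | 2 × 2 = 4 | 2 × 2 = 4 | 3.5 × 1 = 3.5 |
| 3 eggs | 3 | 2 × 3 = 6 | 2 × 3 = 6 | 2 × 2 = 4; 3.5 × 1 = 3.5; 5.5 × 1 = 5.5 |

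That is three ties and four inversions. Two inversions depend on midpoint coding: with the upper ends of the ranges, 4 × 1 = 4 ties with the 2-egg eater and 6 × 1 = 6 ties with the 3-egg eater. The other two hold under either coding, because a score of 6 exceeds both 4 and the whole 3–4 range. If item 1 alone were used for ranking, the floor would produce only ties in frequency.

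**Step 2: which group is touched.** The floor never produces a score above 6, on a scale that runs to 14 × 3 = 42. It reaches the high group only if the upper-quartile cut is about 6 eggs/week or lower.

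**Step 3: illustration of size.** The documents give no intake distribution, so one is assumed. A share p eats eggs once a week. The rest split 30/30/18/17/5% over the five printed frequencies, portions split 30/50/20% over 1/2/3 eggs, and ties are broken at random.

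By hand at p = 10%:
- Once-weekly eaters: 48 × 0.10 = 4.8 (1.44 eat 1 egg, 2.4 eat 2, 0.96 eat 3). All belong in the true lowest 12.
- Scored below 4: 1.44 + 3.89 (2 × 1) + 3.89 (3.5 × 1) = 9.22, leaving 12 − 9.22 = 2.78 places.
- Tied at 4: 6.48 (2 × 2) + 2.4 = 8.88 people for 2.78 places, so 2.4 × (1 − 2.78/8.88) = 1.65 are lost.
- The 0.96 scored 6 are also lost. Total 2.61 of 12, about 22%.

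Simulation of 48 subjects agrees:

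| Assumed share once weekly | Low group misplaced | High group misplaced |
|---|---|---|
| 5% | 10% | 0% |
| 10% | 20% | 0% |
| 20% | 34% | 0% |
| 30% | 35% | 0.1% |

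Part of the low-group figure comes from ties.

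**Step 4: worst-case effect on the contrast.** At 12 v 12, 80% power needs a standardised difference of 1.20 (two-sided 0.05). If a fraction m of the low group had the high group's mean, the difference would shrink to (1 − m) × 1.20. With m = 10%, 20% and 30% that is 1.08, 0.96 and 0.84, giving power of 72%, 61% and 50%. People misplaced by the floor actually come from just above the low cut, so the real loss should be smaller.

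**The case against.** The best defence is that the person most plainly caught by the floor, eating 1 egg once a week, still receives the lowest possible score and stays at the bottom, tied. Inversion needs 2 or 3 eggs on a single weekly occasion and a multiplicative score that no section states. That is correct, and it limits the point to possible misplacement near one cut. It does not remove it: the form still elicits a false answer, and a tie at the cut with no tie rule leaves membership undetermined.

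Other text also softens the point. The 40-subject plan (Statistical procedures, Analyses) recognises FFQ self-report error and adds a sensitivity analysis on observed egg consumption, but the current SAP does not repeat it. If the quartiles were formed from RFPM, as hypothesis 2 can be read, the floor would not matter for grouping; primary outcomes 2 and 4, however, name the FFQ. Telephone screening question 17 records eggs per week without a floor but is not tied to the quartiles.

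A reader might also infer that pooling whites and substitutes in item 1 mis-ranks both groups, or biases the saturated-fat comparison against hypothesis 2. The documents support neither. Items 3 and 4 collect the shares needed to remove whites and substitutes, and nothing says they will be ignored; when the simulation applies them, misplacement from this source is 0%. The gap is an unstated scoring rule. The hypotheses speak of egg consumption without restricting it to whole eggs, and no figure on egg-white eaters or their fat intake is given.

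**Conclusion.** The concern holds in a limited form. As printed, item 1 cannot record an intake that the eligibility criteria admit, so membership of the low group in primary outcomes 2 and 4 and secondary outcome 6 can be wrong or undetermined near the bottom-quartile cut. The high group is essentially untouched by the floor.

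The size is unknown. The 10% to 35% range for the low group follows from assumed distributions and an assumed scoring rule; it is not an estimate for this trial. If no enrolled subject eats eggs as rarely as once a week, the effect is nil. The conclusion also assumes that the extracted answer list is complete. It looks complete, but a line lost in extraction cannot be fully excluded.

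**What to change.** Add a once-a-week answer to Appendix F, item 1, so that the scale covers the eligible range. This costs one line on a form and adds no visit or procedure.

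With the same amendment:
- State the scoring rule in Procedures, section F, and under primary outcomes 2 and 4: item 1 × item 2, the numeric code for each class, whether the item 3 and 4 shares are used to remove whites and substitutes, and how ties at a cut are resolved. The shares are in quarters, so a whole-egg count would be approximate.
- Carry the observed-intake sensitivity analysis from the 40-subject plan into the current SAP.
- Reconcile hypothesis 2, the primary outcomes and the SAP on whether FFQ or RFPM defines the quartiles.

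Screening question 17 should not break ties in a whole-egg count, because it does not separate whites from whole eggs. These additions take a few sentences and need no new data.
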